There are approximately 29,000 children and young people living in the UK with T1D (Juvenile Diabetes Research Federation (JDRF), 2018). The numbers of patients using Dexcom CGM appears to be on average 11% of this population. The number of dietitians, working in paediatric diabetes, is typically 0.5 whole time equivalent per 100 patients (National Paediatric Diabetes Audit, 2019) resulting in approximately 180 paediatric diabetes dietitians working in the UK. Contact with dietitians, to date, suggests it may be possible to gain agreement from approximately 18% of dietitians who are contacted directly. These dietitians would be managing an estimated 5220 patients. Assuming 11% of these use Dexcom CGM then an approximate number of participants that could be recruited is 572 resulting in approximately 18 participants per dietitian. An average of 13-14 participants per dietitian would keep the workload to an average of no more than two working days. The time required for the researcher to contact participants, download and analysis data and food diaries is estimated to be 90 - 120 minutes per participant. For 435 participants this is the equivalent of 75-100 working days which is achievable.

Methodology

Baseline data

In order to make comparisons between relevant variables and glucose levels, the following baseline data will be collected from the dietitians and sent to the researcher, along with the artificial identifier on the Excel spreadsheet as discussed earlier at the stage of recruitment of participants:

- Parent's email address
- Sex, date of birth and recent weight and height (for calculation of BMI and BMI centile)
- Date of diagnosis of T1D
- Last four HbA1c
- Total daily insulin dose (TDD)
- Percentage basal/bolus (if known)
- Insulin: carbohydrate ratios (ICR) and Insulin Sensitivity Factor (ISF)
- Current insulin regimen (including type of insulin prescribed and if applicable type of insulin pump i.e. open or closed loop)

Glucose measurement

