Data on interstitial glucose will be collected via Dexcom CGM. The Dexcom CGM data will be accessed by registering a research 'Clarity Clinic' with Dexcom CLARITY[®] Clinic Portal (Dexcom In, San Diego, CA, USA) with the researcher becoming the administrator of this clinic. Once the managing dietitian has obtained each participant's consent, the participant's parent's email address will be sent to the researcher along with the baseline information/data as described above. The researcher, as administrator of the Clarity Clinic account, will then invite the participant, via email, to be added to the clinic. Once the invite has been accepted, it will stand for the period of the recording i.e. until the participant's questionnaires been received unless the participant decides to withdraw from the study. Once the participant has submitted their last questionnaire, they will be removed from the Dexcom CLARITY[®] Clinic Portal.

Survey questionnaires and photographic food diaries

Following the provision of CGM data, participants will be asked to complete the questionnaires using 'online survey'. Participants will be asked to photograph their breakfast meal and drinks and email along with provide information after breakfast and in the evening, as per the questionnaire presented in Appendix 14 and 15. The CGM data will be collected throughout this time as discussed above.

The food consumed at breakfast will be analysed using Diet Plan 7, a nutrient analysis programme based on the UK food composition tables (Public Health England, 2014). This will provide a calculation of energy and macro and micronutrient intake and allow the accuracy of carbohydrate calculations to be assessed. Where possible, the glycaemic index of the breakfast will be calculated. The analysis from this will be transferred into a CSV file and saved as an Excel spreadsheet as presented in Appendix 16.

Recruitment for Dexcom CGM DATA only

As per Amendment 273640.10, dated 15/05/2021, participants can be recruited to provide CGM data only. This amendment as submitted in order to attempt to obtain large quantities of CGM data as recruitment to the study has been slow. Some families have reported to the recruiting dietitians (Principal Investigators) that they have been reluctant to join because of the time commitment required for completing the survey questionnaires.

Outcome measures

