The researcher will set up a research clinic on Dexcom CGM Clarity which is accessed via the internet and is password and username protected. The researcher, as administrator of this clinic, will then invite the participants, via their parent's email address, to join the clinic. This a standard way of accessing Dexcom CGM data. The invite will include the artificial identifier, and this is the identifier that will be visible when the data is accessed and not the name of the participant. For the invite to work it must include the participant's date of birth for verification purposes. Email addresses and date of birth will be recorded in the baseline information spreadsheet and this will be stored on the NHS Highland laptop. Dexcom have their own security management and personal information is transmitted in encrypted form. CGM data will transferred to a CSV file, saved as an Excel file and stored on an NHS Highland laptop. An example of this in presented in Appendix 17. As consumers of Dexcom CGM the participants will have access to the Dexcom, Inc Privacy Policy which complies with the GDPR) 2016.

(https://www.dexcom.com/en-GB/linked/documentservice/PrivacyPolicy).

Collection, storage and transfer of data - survey questionnaires

The researcher plans to use Jisc 'Online Surveys' (formerly BOS). The University of Stirling subscribes to this service and the researcher has a unique username and password for accessing this, known only to the researcher. Jisc is registered with the Information Commissioners Office (ICO) (registration number Z9546606) and meets the requirements of GDPR (https://www.onlinesurveys.ac.uk/gdpr-and-online-surveys/) and is certified to ISO 27001 (https://www.jisc.ac.uk/about/certification). All survey responses are collected over encrypted SSL (TLS) connections and deleted after three months. The university GDPR statement is added to all the survey questionnaires. Responses to the survey will be transferred to a CSV file then saved as an Excel file on the NHS Highland laptop. An example of this is presented in Appendix 18 and 19.

Collection, storage and transfer of data - Photo food diaries

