The participants will be asked to only photograph the meal and not include anything else that may be identifiable in the photograph. Instruction on how to do this is provided in a separate sheet as presented in Appendix 20. The photographs will be emailed to the researchers NHS mail email account. These will be downloaded and saved to the NHS Highland remote secure

server as described above. Should any identifying information be included in the photograph this will be deleted from the photograph before it is saved.

Collection, storage and transfer of data - Nutritional analysis

The breakfast meals will be analysed using DietPlan 7 which will be accessed via an NHS Highland desktop. Data entered will be pseudonymised, using the artificial identifier as described below. The analysis will be transferred to a CSV file, saved as an Excel file and emailed via NHS mail to be saved on the NHS Highland laptop.

Data ownership

It is anticipated that new data, arising from the study, and the associated intellectual property will be owned jointly by the University of Stirling and NHS Highland with a sharing agreement. Dexcom were contacted about this, via email, in January 2020 and have failed to respond.

Destruction of data

The Dexcom Clarity clinic only stores CGM data for three months. Once these data have been collected for the period of the study, the Dexcom research clinic will be closed. Any transferred data will be stored on the NHS Highland secure remote server for 10 years before being deleted. Responses to surveys are backed up on the Online Survey system for three months then they are deleted and destroyed.

Reviewing the data management plan

At the suggestion of the NHS Highland Research and Development office, a Data Management Committee will be set up. Meetings will be arranged at regular intervals to ensure the data management plan is adhered to and to address any difficulties.

Expected outcomes

The aim of this study is to describe the distribution and dispersion of glucose variability and postprandial hyperglycaemia after breakfast and establish comparisons of these between variables obtained from baseline information and nutrient analysis. It is hoped this will formulate a quantitative research question and power calculation for a sample size for a intervention trial to test different meals at breakfast.

Dissemination of results

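### One researcher handles both the glucose traces and the breakfast food records, and the plan neither masks the meal coding nor says whether it precedes sight of the glucose

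*Combined protocol and SAP*

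**What the plan says.** The roles have to be assembled from several sections of the protocol.

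- **Workload.** Sample size estimates "The time required for the researcher to contact participants, download and analysis data and food diaries" as a single block of time per participant.
- **Glucose.** Glucose measurement sets up a research Clarity clinic "with the researcher becoming the administrator of this clinic". Access stands until the last questionnaire is in.
- **Photographs.** Under Photo food diaries: "The photographs will be emailed to the researchers NHS mail email account".
- **Nutrient coding.** Under Survey questionnaires and photographic food diaries: "The food consumed at breakfast will be analysed using Diet Plan 7". The output has a second use: "This will provide a calculation of energy and macro and micronutrient intake and allow the accuracy of carbohydrate calculations to be assessed". On glycaemic index: "Where possible, the glycaemic index of the breakfast will be calculated".
- **Order.** The same section says: "Following the provision of CGM data, participants will be asked to complete the questionnaires". CGM collection then continues through the survey week. Study design adds three months of retrospective CGM.
- **Identifier.** For the CGM record, the artificial identifier is what the researcher sees: "this is the identifier that will be visible when the data is accessed and not the name of the participant". Nutritional analysis puts the artificial identifier on the food record too.

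No section in the supplied text calls for a coder masked to glucose, a lock on the coding, duplicate coding, or a written rule for portion size or glycaemic index.

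**The concern.** Meal composition is the exposure in the fifth objective and in the matching secondary outcome; four-hour glucose is the response. Estimating a portion and choosing a food code involve judgement. So does deciding when a glycaemic index is possible, since no rule is given. A coder who has seen a steep rise after breakfast may lean towards a larger portion, or conclude that the family under-counted the carbohydrate. Error in the exposure would then be correlated with the outcome, and recruiting more children would not remove it.

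The consequence reaches beyond this study. Data analysis and Expected outcomes say the results should help frame the question and sample size of a later breakfast intervention trial. A distorted food-glucose association would carry over into that design.

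**Working it through.** **Step 1: who does what.** The researcher runs the portal, receives the photographs and has both the download and the food diaries in the workload estimate. The sentences on DietPlan 7 are passive and name no operator. That the researcher is the coder is therefore an inference, though a strong one, because nobody else is named.

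**Step 2: in what order.** The protocol puts the provision of CGM data before the questionnaires. This can refer only to access and earlier data, since the survey-week trace does not exist until those breakfasts have been eaten. Whether coding precedes or follows sight of that trace is not stated.

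**Step 3: what separates the two records.** Nothing does. The shared identifier serves confidentiality, and the Data Management Committee oversees the data management plan. Neither masks the coder.

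**Step 4: size when there is no true association.** The plan gives no figure to reproduce. These inputs are assumptions: breakfast carbohydrate C has SD 20 g, four-hour mean glucose G has SD 3 mmol/l, and the two are independent. Coded carbohydrate is C + k(G − mean G), where k is the drift in g per mmol/l. Then:

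- slope of G on coded carbohydrate = 9k / (400 + 9k²)
- correlation = 3k / √(400 + 9k²)

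| k | slope (mmol/l per g) | correlation | difference per 30 g (mmol/l) |
|---|---|---|---|
| 0.5 | 4.5/402.25 = 0.0112 | 0.075 | 0.34 |
| 1 | 9/409 = 0.0220 | 0.148 | 0.66 |
| 2 | 18/436 = 0.0413 | 0.287 | 1.24 |

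**Step 5: direction when there is a true association.** Keep the same SDs and take k = 0.5.

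- True slope −0.03: cov(C, G) = −0.03 × 400 = −12. Covariance with coded carbohydrate = −12 + 0.5 × 9 = −7.5. Variance = 400 − 12 + 2.25 = 390.25. Observed slope = −7.5/390.25 = −0.019, nearer zero than the truth.
- True slope +0.03 with additional random portion error of SD 15 g (assumed): covariance = 12 + 4.5 = 16.5. Variance = 400 + 12 + 2.25 + 225 = 639.25. Observed slope = 0.026, again nearer zero than the truth.

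The net direction therefore depends on the true association and on the other coding error.

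**The case against.** The strongest case against runs as follows.

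- **The coder is inferred, and discretion may be small.** The morning questionnaire also asks what was eaten and drunk, and its content is in an appendix not supplied, as are the nutrient sheet and the photograph instructions. Family-reported quantities could leave little to judge. This stands as a limit on how much drift is plausible. It does not remove the point, because reported quantities narrow the coder's discretion without masking the coder.
- **The size is assumed.** Both SDs and k come from outside the documents. The largest figure needs k = 2, which is 12 g of drift for a trace 2 SD (6 mmol/l) above average. This stands: the table shows sensitivity, not evidence of bias.
- **The study is descriptive and the food comparisons are secondary.** This is true and limits the priority. It does not protect the comparisons, because a described association is distorted in the same way as a tested one.
- **The coder knows about glycaemic control anyway.** Baseline data include the last four HbA1c values. This stands as a residual weakness of any lock. HbA1c describes the child's average control, however, and not the response to a particular breakfast.

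**Conclusion.** The plan leaves meal coding open to influence from the glucose result. The fifth objective, the matching secondary outcome and the assessment of carbohydrate counting are exposed. Under the assumed SDs and drift, and with no true association, the spurious correlation is about 0.08 to 0.29. This is an inexpensive improvement worth making, not a fault that undermines the study.

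A reader might infer four stronger things that the documents do not support:

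- **That the plan prescribes viewing the trace before coding.** It orders portal access before the questionnaires and is silent on the rest.
- **That the bias always runs away from the null.** This follows only when the true association is taken as zero; Step 5 shows movement towards the null.
- **That the main results are compromised.** The primary outcome and the time-in-range measures are device readings that food coding does not alter, and CGM-only participants have no meals to code.
- **That bias has occurred.** The documents show an opportunity for it and nothing more.

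**What to change.** Add one paragraph to the section on survey questionnaires and photographic food diaries, fixing this order of work for each child:

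1. Complete the DietPlan 7 coding (nutrients, glycaemic index, carbohydrate-count error) from the photographs and morning surveys. Leave the evening survey out of this step, because its insulin and carbohydrate adjustments hint at the glucose response.
2. Lock the coding with a date stamp before opening that child's survey-week CGM data or the three-month retrospective data. The retrospective trace matters because it may show the child's usual pattern after breakfast.
3. Export the CGM file unopened before the child is removed from the portal. Check completeness by file size or record count only. At 5-minute intervals a full survey week is 7 × 288 = 2,016 readings.
4. Log a reason for any later change to a meal code.

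The same researcher, data and software suffice. The cost is that glucose values cannot be reviewed until that child's meals are coded, and problems that a record count does not reveal may surface only after portal access has ended. The coder will still know the baseline HbA1c. For children already coded, record whether the trace had been seen first, so that the food comparisons can be reported with that caveat.

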It is known that chronic hyperglycaemia causes increased risk of diabetic complications. It is possible that both glucose variability and postprandial hyperglycaemia are independent risk factors for this as well. There is some evidence that glucose variability and postprandial hyperglycaemic are common occurrence for children who have T1D. However, there is a paucity of published data on the prevalence of postprandial hyperglycaemia after breakfast in children and young people with T1D and no evidence-base for how to manage this phenomenon. The need for long-term studies to examine glucose variability from CGM data and, for closer examination of postprandial glucose variability to elucidate methods to reduce this, has been highlighted (Tansey *et al.* 2016). Although this applies to all meals, focusing on minimising postprandial hyperglycaemia after breakfast is paramount. This can help ensure good control through the morning and rest of the day when children are at school and actively learning (Tansey *et al.* 2016).

Aim:

To describe the distribution and dispersion of glucose variability and postprandial hyperglycaemia following breakfast, in children and young people with type 1 diabetes (T1D), using measurements from Dexcom CGM.

Objectives:

- To determine the glucose variability diurnally and nocturnally and in the four-hour postprandial breakfast period using measurement of 'time in range', 'time above range' and 'time below range'.
- To determine the variability of glucose excursion, level and peak and the recovery time in the four-hour postprandial breakfast period.
- To determine the number and percentage of participants who achieved internationally agreed pre and postprandial glucose targets at breakfast time.
- To describe comparisons between all the above measurements and the variables of sex, age, disease duration, BMI, HbA1c, insulin dose/sensitivity and insulin regimen.
- To describe comparisons between all the above measurements and food compositions taken in the breakfast meal.
- To describe comparisons between the above measurements and carbohydrate and insulin adjustments, fluid intake and activities that took place during in the four-hour postprandial breakfast period.

Study design

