Primary and secondary outcome measures will be based on international guidelines and consensus DiMegloi *et al.* 2018; Battelino *et al.* 2019) of the metrics and target glucose levels to be used in CGM analysis in clinical practice. These are agreed to be:

Metrics:

- Mean glucose
- Glucose variability (GV) % coefficient of variation (COV) target ≤36%
- Time in range (TIR) % and time spent between 3.9-10mmol/I
- Time above target (TAR) % and time spent >10.1-<13.9mmol/l) and >13.9mmol/l
- Time below range (TBR) % and time spent 3.0-3.8mmol/l and <3mmol/l

Target glucose levels:

- TIR % of readings >70% or 16hr 48min
- TAR % of readings <25% or <6hr high and <5% 1hr 12min very high
- TBR- % of readings <4% or <1hr low and <1% or <15min very low

Primary outcome measure:

• Mean glucose (mmol/l) in the four-hour postprandial breakfast period calculated from the CGM measurements at 5 minutes intervals.

Secondary outcome measures – post prandial period:

• Number and percentage who had pre-prandial glucose in target Mean peak glucose level (mmol/l), mean time to peak (mins), mean time to recover (to pre-prandial levels) (mins) in the four-hour postprandial breakfast period

- TIR, TBR and TAR (% and time) in the four-hour postprandial breakfast period
- Comparisons of the above measurements between cohorts and breakfast meal compositions and drinks, snacks taken in the morning and activities and insulin adjustments taken in the 4-hour postprandial period.

Secondary outcome measures – glucose variability:

• TIR, TBR and TAR (% and time) between the hours of 06.00-22.00, 22.00-06.00 and 24-hour period.

Data analysis

This will be a mix of univariate, bivariate and multivariate analysis as this is best suited to describing, summarising and visualising these data. Outputs will include the distribution of glucose levels and diurnal, nocturnal and post-breakfast variability to determine the spread and dispersion of the data. As well as providing new evidence on this phenomenon, it will also assist in determining required sample size for any subsequent investigation including an intervention testing of effects on interstitial glucose levels arising from different food intakes.

Safety considerations

Recruitment/consent

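### The time-above-range bands leave readings of exactly 10.1 and 13.9 mmol/l in no category; coded literally on 0.1 mmol/l readings, TIR, TAR and TBR would sum to about 98-99%, not 100%

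*Combined protocol and SAP*

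**What the plan says.** The Metrics list under Outcome measures defines five glucose bands in three lines:

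- In range: "Time in range (TIR) % and time spent between 3.9-10mmol".
- Above range: "Time above target (TAR) % and time spent >10.1-<13.9mmol/l) and >13.9mmol/l".
- Below range: "Time below range (TBR) % and time spent 3.0-3.8mmol/l and <3mmol/l".

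The bands feed two sets of secondary outcomes. One is "TIR, TBR and TAR (% and time) in the four-hour postprandial breakfast period"; the other is "TIR, TBR and TAR (% and time) between the hours of 06.00-22.00, 22.00-06.00 and 24-hour period". They also carry the first objective, which is to describe glucose variability "using measurement of 'time in range', 'time above range' and 'time below range".

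The primary outcome is mean glucose over the four hours after breakfast, from readings at 5-minute intervals. It does not use the bands. On data handling, the protocol says that "CGM data will transferred to a CSV file, saved as an Excel file and stored on an NHS Highland laptop". The documents do not say how readings are rounded, which band takes a value lying on a limit, or whether the bands are computed by the researcher or taken from the device software.

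**The concern.** Time in, above and below range should partition the readings, so that each falls in exactly one band and the percentages sum to 100. The bands as written do not. Time in range stops at 10 and the first upper band starts strictly above 10.1. The two upper bands then meet at 13.9 with a strict sign on each side.

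On readings held to 0.1 mmol/l, every lost reading lies above range. The error therefore runs one way: time above range is understated, while time in range and time below range are correct. The study's purpose is to describe distribution and dispersion, so the band limits are the measurement itself. An analyst who follows the text would report categories that do not add up, and two analysts who patch the gap differently would report different splits between the upper bands.

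**Working it through.** **1. The plan's own figures.** The percentage targets convert correctly to time over 1,440 minutes: 70% = 1,008 min = 16 h 48 min; 25% = 360 min = 6 h; 5% = 72 min = 1 h 12 min; 4% = 57.6 min (given as under 1 h); 1% = 14.4 min (given as under 15 min). The fault is in the band limits, not in these conversions.

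**2. Which values have no band.** Each value 2.2, 2.3, ..., 22.2 mmol/l (201 values) was tested against the bands as written: x < 3; 3.0 ≤ x ≤ 3.8; 3.9 ≤ x ≤ 10; 10.1 < x < 13.9; x > 13.9. Exactly two values meet none of these, 10.1 and 13.9. No value meets two. The low bands join time in range without a gap at this resolution.

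**3. How many readings that is.** The documents give no glucose distribution, so one is assumed: lognormal, means 8.5, 9.5, 10.5 and 11.5 mmol/l, CVs 33, 36, 39 and 42%. The protocol's CV target of 36% lies within that range. With F the distribution function,

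s² = ln(1 + CV²), m = ln(mean) − s²/2, F(x) = Φ((ln x − m)/s).

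The unassigned share is [F(10.15) − F(10.05)] + [F(13.95) − F(13.85)].

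Example, mean 9.5 and CV 36%: s² = ln(1.1296) = 0.1219, s = 0.3491, m = 2.1904.

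- At 10.1: Φ(0.3641) − Φ(0.3358) = 0.6421 − 0.6315 = 1.06%.
- At 13.9: Φ(1.2751) − Φ(1.2545) = 0.8989 − 0.8952 = 0.37%.
- Total: 1.43%.

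Over all 16 combinations:

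| Quantity | Range |
|---|---|
| Share at 10.1 | 0.80-1.23% |
| Share at 13.9 | 0.21-0.67% |
| Unassigned in total | 1.06% (mean 8.5, CV 42%) to 1.87% (mean 11.5, CV 33%) |
| Sum of the five bands | 98.13-98.94% |
| Minutes per 24 h (× 1,440) | 15.3-26.9 |
| Share of total time above range (24.8-60.2% of readings) | 2.8-4.8% |

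If the same distribution held in every window, the loss would be 10.2-17.9 min in 06.00-22.00 (× 960), 5.1-9.0 min in 22.00-06.00 (× 480) and 2.6-4.5 min in the four hours after breakfast (× 240). A single four-hour window holds 240/5 = 48 readings, so each unassigned reading lowers that window's time above range by 1/48 = 2.1 points.

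**4. Sensitivity to the assumption.** With normal, lognormal and gamma shapes, means 8-11 and CV 30-45% give 0.91-1.99 points. The widest grid (means 7-13, CV 25-45%) gives 0.45-2.26 points; values below 1 occur mainly at means of 7-7.5 mmol/l.

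**5. If readings are kept unrounded.** The value 13.9 becomes a single point of practically no weight, and the gaps are the intervals 10.0-10.1 and 3.8-3.9. On the grid in step 3, F(10.1) − F(10.0) = 0.81-1.23% and F(3.9) − F(3.8) = 0.02-0.54%, together 1.09-1.36%. Part of the shortfall then lies outside time above range.

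**6. Effect on a comparison of groups.** At CV 33%, true time above range is 24.8% at mean 8.5 and 60.2% at mean 11.5, a difference of 35.4 points. The losses are 1.18 and 1.87 points, so the reported difference would be 35.4 − (1.87 − 1.18) = 34.7 points.

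**The case against.** The best reply is that the intent is clear and the consequence slight. Given a range ending at 10, a reading of 10.1 can only be above range, and so can 13.9. The line has an unmatched bracket, which suggests a typing slip, and the outcomes are said to follow an international consensus. Device software may do the banding, and a check of the total would expose the gap.

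Much of this is fair, but it does not make the written bands correct. The text is the only rule the documents give, and nothing in them says that software will do the banding. A lost sign in text extraction is unlikely, since the ≤ in the CV target survives in the same list. Even on the generous reading, which upper band takes 13.9 stays open.

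The objections to the size carry more weight:

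- The assumed grid is not from the documents, and a well-controlled cohort would lose nearer 0.5-1 point.
- The per-window minutes rescale one distribution, although the protocol's background describes different night and day patterns. They are illustrative, the night figure especially.
- The loss as a share of the first upper band depends on who owns 13.9. It is 4.9-5.8% if 13.9 belongs there. Counting only 10.1 over the same denominator, it is about 3-5% (1.19/37.9 = 3.1% at mean 11.5, CV 33%; 0.96/20.3 = 4.7% at mean 8.5, CV 33%).
- Limits written as contiguous inequalities would close the gaps without a rounding rule.

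**Conclusion.** The point holds: followed literally, the bands do not partition the readings. That 10.1 and 13.9 are the two orphaned values follows from the text alone, once readings are held to 0.1 mmol/l. The size, about 1-2 points for means of roughly 8-12 mmol/l, rests on an assumed glucose distribution and is nearer 0.5-1 point at means of 7-7.5.

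This is a minor correction. It concerns secondary outcomes only. No effect is claimed on the number of children meeting a target; any such effect would be confined to those close to one.

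**What to change.** - Rewrite the bands so that every reading falls in exactly one, for example: below 3.0; 3.0-3.8; 3.9-10.0; 10.1-13.9 inclusive; above 13.9.
- Have the sponsor confirm which upper band takes 13.9, since the present signs do not say. On the grid above, the choice moves 0.2-0.7 points between the two upper bands and leaves total time above range unchanged.
- State that readings are rounded to 0.1 mmol/l before banding, or write the limits as contiguous inequalities that hold at any resolution.
- If software-computed bands are used, say so and make the protocol limits match them.
- Check that the five percentages sum to 100% in each of the four windows.

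The cost is a change of symbols in one line, one sentence on rounding and one data check. The readings are kept as exported files, so any banding already done can be repeated without new data.
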